## **BACKGROUND**

### **Preterm birth**

Prematurity is a leading cause of perinatal morbidity and mortality affecting 12% of approximately 4 million deliveries in the United States. Though the etiology of preterm labor is largely unknown, it is defined as regular contractions of the uterus resulting in changes in the cervix that starts before 37 weeks of pregnancy. Preterm birth that occurs between 20 to 37 weeks of pregnancy, due to preterm labor and premature rupture of membranes, continues to be a challenging concern for the practicing obstetrician. Since the fetus is not yet fully developed before 37 weeks of pregnancy, health problems associated with preterm birth include a variety of acute and chronic health/developmental deficiencies. Among these are acute respiratory, gastrointestinal, immunologic, CNS, hearing and vision issues, as well as cerebral palsy, cognitive, visual, hearing, behavioral, social-emotional, learning, health, and growth problems.

To mitigate the complications of preterm birth, tocolytics, a group of medications that are purported to prevent preterm delivery, are utilized. Tocolytics belong to a number of pharmacological families, including non-steroidal anti-inflammatory drugs (NSAID),  $\beta$ 2-agonists and calcium channel blockers. Though this group of medications may postpone delivery by 48 hrs., none of the tocolytics have been proven to be effective in the treatment of preterm labor and improve neonatal outcomes.

### **Current Tocolytic Therapy**

Nifedipine is a commonly used calcium channel blocker used for tocolysis in the treatment of preterm labor. Its mechanism of action is prevention of the influx of extracellular calcium ions into the myometrial cells of smooth muscles within the pregnant uterus. It has been studied in 38 randomized controlled trials involving 2511 women. Compared to placebo, nifedipine significantly decreases delivery within 48 hours, RR 0.3 (0.21-0.43). When compared to other tocolytic agents including betamimetics, nitroglycerin, non-steroidal anti-inflammatory agents, magnesium sulfate and oxytocin receptor antagonist, nifedipine had similar results in prolongation of pregnancy and neonatal outcomes.

Indomethacin is another commonly used tocolytic agent from the NSAID family. The role of prostaglandins in the initiation of labor is well documented. Indomethacin is a non-selective prostaglandin synthetase inhibitor that suppresses the production of prostaglandins, thus, ultimately, inhibiting preterm labor. Prostaglandins are produced in multiple compartments of pregnancy including the cervix, amion, chorion and uterine tissue. Numerous randomized controlled trials comparing indomethacin to either placebo or other tocolytic agents have shown a significant delay in delivery of up to 48 hours in 90-94% and up to 7 days in 75% of cases when indomethacin was used.

Nifedipine has been compared to indomethacin in 2 trials. In 2011, Kashanian randomized 40 women to nifedipine and 39 to indomethacin for the treatment of preterm labor. Only 33

women were included in the analysis, (23 nifedipine and 10 indomethacin). There were similar rates of delay in delivery and gestational age at delivery in both groups. In 2014, Klauser conducted a randomized controlled trial (RCT) of 301 women for the treatment of preterm labor; 114 received nifedipine, 90 magnesium, and 90 indomethacin. The gestational age at delivery, prolongation of pregnancy >7 days were similar between groups. Maternal adverse effects were reported in all groups.

### **Combination Therapy in Medicine**

Since the etiology of preterm labor is multifactorial, single-targeted agents for complex medical conditions may be suboptimal treatment and may explain why RCTs involving single tocolytics have not improved the neonatal outcome. Other disciplines of medicine routinely use combination medication therapy that include varying mechanisms of action to treat many medical conditions. For instance, initial treatment of myocardial infarction includes aspirin, a beta blocker and nitrate. In addition, chemotherapy often involves multiple agents. Moreover, hybrid medications are often prescribed for hypertension (i.e. valsartan-hydrochlorothiazide), pain (i.e. acetaminophen-oxycodone) and diabetes (i.e. glipizide-metformin). In certain conditions in pregnancy, this same concept occurs including broad spectrum antibiotics for postpartum endometritis (gentamicin and clindamycin), preterm premature rupture of membranes (ampicillin and erythromycin), and postoperative pain (i.e. opioid with non-steroidal anti-inflammatory). But for preterm labor, current practice includes single agent tocolytic therapy.

### **Combination Tocolytic Therapy in Pregnancy**

Eleven RCTs have compared combinations of tocolytic agents. The majority of studies included IV ritodrine and terbutaline. In 1978, indomethacin in combination with IV ritodrine was compared to IV ritodrine alone involving 208 women. There was a statistically significant decrease in the number of women delivering before 37 weeks in the combination group, RR 0.7 (CI 0.5-0.97). A recent study of combination salbutamol (n=38) and nifedipine was compared to nifedipine alone (n=38). There was no difference in the mean gestational age at or interval to delivery. Those with combination had more adverse effects. There are no studies that compare nifedipine combined with indomethacin to nifedipine alone.

### **Pharmacogenomics and Personalized Medicine**

Pharmacogenomics is the application of genomic and molecular data in order to better target the delivery of health care, facilitate the discovery and clinical testing of new products, and/or help determine an individual's predisposition to a particular disease or condition. [Shastry] Personalized medicine is multifaceted, and includes genetic factors, historical factors (e.g. family history, and personal medical and obstetric history), and environmental factors (e.g. concurrent medication use or exposure to tobacco smoke), and synthesizes this information with the overall goal of individualizing medical care and treatment to optimize outcomes. The goal of personalized medicine is to provide the 'right dose of the right drug for the right patient at the right time'. [Shastry] The application of pharmacogenomics knowledge has the potential to individualize medications and doses, and may minimize adverse effects.

Pharmacogenomic information is currently provided by the US Food and Drug Administration (FDA) for over 130 drugs. [FDA] Many of the medications with pharmacogenomic labeling are

commonly prescribed; it has been estimated that 25% of all outpatient prescriptions includes one of these medications.[Freuh] Currently, more than 50 genes have been implicated as genomic biomarkers; most commonly, these biomarkers pertain to polymorphisms in cytochrome P450 (CYP) enzyme metabolism. Polymorphisms in CYP enzymes are relatively common. For example, CYP2D6 is estimated to metabolize approximately 25% of drugs, and is known to be very polymorphic. Over 70 alleles have been identified in this gene, and as a result, CYP2D6 activity ranges widely, even within populations.[Zhou, Zhou] Up to 8% of European Americans will be identified as 'poor metabolizers'. Given that this is only one hepatic enzyme involved with metabolism, this attests the importance of developing companion diagnostic tests to accompany pharmaceuticals. Pharmacogenetic evidence exists in asthma, anticoagulation, antibiotics, and oncology.

### **Pharmacogenomics of indomethacin and nifedipine**

Pharmacogenetic studies in pregnancy and pregnant women are limited. However, there are pharmacogenetic information for both indomethacin and nifedipine, which may impact the treatment for preterm labor. The polymorphic CYP3A family of metabolic enzymes in the liver metabolizes nifedipine. One small study of 14 women receiving nifedipine tocolysis genotyped participants for CYP3A5, and analyzed nifedipine concentration over time. These investigators found that the CYP3A5 genotype correlated with clearance of nifedipine: individuals with high CYP3A5 expression metabolized nifedipine more quickly and had lower serum levels of nifedipine across the study period.[Haas] In another pilot study of 20 pregnant women, Haas et al. examined 20 pregnant women receiving nifedipine for preterm labor. The CYP3A5 genotype was found to correlate with nifedipine levels. Women with the high-expression genotype were again found to have lower nifedipine levels. Importantly, this study also showed that individuals with high expression of CYP3A5 had less improvement in contraction frequency at several time points: after the loading dose, at the steady state, and in the first hour after the study dose.[Haas J Mat] Indomethacin is another commonly used tocolytic. It is metabolized by the polymorphic CYP2C9 and CYP2C19 enzymes in the liver.[ Nakajima]

### **Rationale for this clinical trial**

Our current treatment for preterm labor has not been shown to be effective in prolonging pregnancy sufficiently to improve neonatal outcomes and other treatment strategies are needed. Multiple examples demonstrate that multi-agent treatments are routine clinical practice in other fields of medicine including chemotherapeutics for cancer, multi-therapeutics for myocardial infarction and broad spectrum antibiotics for pneumonia. At this time, it is unclear if a combination of tocolytic medications for preterm labor is more advantageous for women. If pregnancy is prolonged with combined tocolytic therapy, this could directly influence the treatment of preterm labor and potentially improve neonatal outcomes. There currently are no trials of combination regimens using widely used tocolytic agents, such as nifedipine and indomethacin. In addition, the pharmacogenomic profile of indomethacin and nifedipine in a clinical trial has not been investigated in a randomized controlled trial. Thus, we propose a comparative effective trial of nifedipine plus indomethacin vs. nifedipine alone for the treatment of preterm labor.

## Hypothesis

We hypothesize that preterm labor is a multifactorial condition that may respond to a combination of tocolytic agents that function by different mechanisms. Therefore, combination tocolytics may prolong pregnancy compared to single agent therapy.

## Objective

Our objective is to determine whether pregnancy prolongation, defined as the time interval from the initiation of tocolytics to delivery, is significantly longer for women who receive nifedipine plus indomethacin versus those that receive nifedipine alone.

## **RESEARCH DESIGN & METHODS**

### Study Design

We propose an open label, randomized, comparative effectiveness controlled trial of nifedipine alone vs. nifedipine-indomethacin in pregnant women for the treatment of acute preterm labor. Prior studies have confirmed that tocolytic therapy can prolong pregnancy for 48 hours to achieve corticosteroid therapy in women with preterm labor. Thus, administering just a placebo for tocolysis is not justified at this time.

Consenting subjects will be randomly allocated to receive one of two clinically accepted clinical regimens, either nifedipine alone or nifedipine plus indomethacin.

### Inclusion Criteria

We will include pregnant women with singleton or multiple gestation between 220/7 to 316/7 weeks gestation who present with regular uterine contractions defined as at least one contraction every 10 minutes for 30 minutes with at least one of the following:

- cervical change of at least 1 cm or
- cervical dilation of 2 cm at the time of initial exam or
- positive fetal fibronectin and transvaginal cervical length <2.5 cm

These criteria were chosen since these findings are associated with acute preterm labor.

### Exclusion Criteria

We will exclude pregnant women with:

- clinical chorioamnionitis (defined as a temperature of >100.4 F and any of the following: fundal tenderness, maternal tachycardia, fetal tachycardia or purulent vaginal discharge)
- non reassuring fetal heart tones
- suspected placental abruption
- preterm premature rupture of membranes
- prior tocolytic treatment during the past 48 hours
- known adverse effect to indomethacin or nifedipine
- already receiving nifedipine for chronic hypertension

## Recruitment

Recruitment will occur on the Labor and Delivery ward at Memorial Hermann Hospital-Texas Medical Center, Lyndon B Johnson Hospital, Memorial Hermann Memorial City Hospital, Memorial Hermann Pearland Hospital and Memorial Hermann Greater Heights Hospital. All participants will be admitted for hospital care to the antepartum unit or to labor and delivery. Eligible women will be identified after it is deemed necessary by the caring physician to provide medical treatment for preterm labor. Those who meet study criteria will be approached about the study in the admission area/OB triage, antepartum unit or labor and delivery at the time of admission. A member of our research team, either a physician or research assistant/nurse, will obtain written informed consent.

## Randomization

Randomization will be performed based on a computer-generated list that will be created by a non-clinical member of the research team. Randomization will be stratified by site. A permuted block randomization with a random fashion will be used to prevent imbalances between groups. The medication based on the computer generated list will be typed out on a piece of paper with the medication regimen written according to the below regimens. This piece of paper will be placed in an opaque envelope and numbered according to the computer generated list. The opaque envelopes will be kept on the obstetrical unit and be managed by the research team.

## Methods

Women will receive the first dose of either nifedipine-indomethacin or nifedipine after it is determined necessary that the patient will require medications for preterm labor by the caring physician according to clinical management for a 48 hour time period. 48 hours is chosen based on current American College of Obstetrics and Gynecology recommendations, which state that tocolytic therapy should be administered to allow for administration of antenatal corticosteroids and transfer to a tertiary facility. Antenatal steroids have been shown to accelerate fetal lung maturity as well as decrease the incidence of intraventricular hemorrhage and necrotizing enterocolitis. The optimal timing of delivery after administration of corticosteroids is at least 48 hours but less than 7 days after steroid administration. Data will also be collected regarding maternal demographics, pregnancy characteristics, medications administered, length of pregnancy, and maternal/ outcomes and neonatal fetal outcomes.

**Rescue regimen**

If it is determined that either the nifedipine-indomethacin or nifedipine alone is not adequate or adverse effects occur during the treatment of preterm labor, then other tocolytic regimens may be administered according to the managing physicians.

**Pharmacogenomics**

To assess the pharmacogenomic profile, maternal blood (20 ml) will be obtained via venous puncture prior to tocolytic administration, 48 hours after tocolytic administration and at delivery. Cord blood (20 ml) will also be obtained at the time of delivery after delivery of the newborn and prior to delivery of the placenta.

Finally, a myometrial biopsy will be obtained at the time of cesarean section for those women who undergo this mode of delivery. Myometrial biopsies will be obtained from the middle of the upper margin of the lower segment of the uterine incision measuring 4cm x 2cm x 2 cm. The biopsies will be performed by the managing obstetrical physician at the time of cesarean section once the neonate and placenta are delivered. The biopsy specimen will then be placed immediately in cold physiologic saline solutions and brought to the lab. This biopsy will be taken to the lab to test whether different medicine will increase or decrease contractions in the tissue. Once this test is finished, the tissue will be frozen. Thinly cut portions of the frozen tissue will be tested for whether or not the medicines are present or absent within the tissue.

Moreover, a portion of the tissue will be used to create cell cultures to test tocolytic drugs in vitro and determine cellular responses to these drugs.

A placental biopsy will also be obtained after it is delivered measuring 1 cm x 1 cm x 1 cm.

All biopsies and blood collected will be tested for other factors including genes, DNA material or other diagnostic tests. Any samples not used for this study will be stored and used for future research.

All information will be confidential and de-identified. The subject will be coded as a number and a linking log will be used to separate patient information from research data.

### **Primary Outcomes**

The primary outcomes will include the following

- Percentage of women achieving 48 hours pregnancy prolongation

### **Secondary Outcomes**

Secondary outcomes will include the following:

- Percentage of women achieving 7 days pregnancy prolongation
- Number of hours from first dose of tocolytic agent to delivery. The hours will be rounded to the closest day.
- Neonatal outcomes including birthweight, gender, need for NICU admission, length of NICU admission, length of hospital stay, rate of death, intraventricular hemorrhage, necrotizing enterocolitis, culture positive sepsis, neonatal seizures, need for mechanical ventilation, ECMO, CPAP or blow by oxygen and length of mechanical ventilation, CPAP, ECMO or blow by oxygen.
- Pregnancy outcomes including rate of cesarean delivery, clinical chorioamnionitis, preterm premature rupture of membranes, preeclampsia, need for blood transfusion
- Reported adverse effects including headache, nausea, vomiting, acid reflux, maternal hypotension including BP<90/60, maternal tachycardia with heart rate >120, syncope.

Neonatal outcomes will be followed until hospital discharge or day 120 of life.

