### **Data analysis and sample size calculations**

We have conducted a Bayesian power analysis for this study comparing combination therapy with nifedipine and indomethacin versus single agent therapy with nifedipine alone for treatment of acute preterm labor. Our primary outcome is the percentage of women that remain pregnant at >48 hours.

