#### **Design prior distributions:**

Single agent outcome rate: 77% (95% CI: 68%-85%)

Combination outcome rate: 95% (95% CI: 74%-99.9%)

Our clinically important absolute difference (combination % - single agent %) of > 10%. Pr(difference >10%)> level of certainty. Our enthusiastic prior is the same as the design prior above. Neutral prior assumes no difference between two groups, RR=1.0 with 95% CI of 0.5-1.33.

Level of Certainty	N per group	Bayesian Power	
		Enthusiastic prior	Neutral prior
67%	30	0.83	0.77
	40	0.85	0.80
	50	0.85	0.83
75%	100	0.86	0.83
	30	0.80	0.72
	50	0.83	0.79
80%	100	0.84	0.81
	30	0.77	0.68
	50	0.79	0.77
	100	0.84	0.80

For the primary outcome of % of women that remained pregnant > 48 hours, we assumed rates of 77% (95% Credible Interval: 68%-85%) in the nifedipine alone group and 95% (95% Credible Interval: 74%-99.9%) in the nifedipine-indomethacin group. We assumed an absolute risk difference (RD) of 10% between the two groups as the minimum clinically important treatment effect. We are interested in a posterior probability of 67% or more for this effect, i.e. Pr(RD>0.10) > 0.67. We conducted a simulation study to calculate the needed sample size to have 80% power to detect an RD >10% with 67% probability. We used the expected outcome rates to simulate data, and we assumed a neutral prior (meaning no a priori difference between the two groups with a RD centered at 0) for the final analysis. A sample size of n=40 per group will have 80% power of detecting a RD of 10% or more with 67% certainty.

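### The plan's only clock for prolongation starts at treatment and no analysis set is defined, so a woman randomised but not dosed has no time zero and no stated place in the denominator

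*Combined protocol and SAP*

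**What the plan says.** The Objective defines prolongation as "defined as the time interval from the initiation of tocolytics to delivery" and frames the comparison as "women who receive nifedipine plus indomethacin versus those that receive nifedipine alone". The Primary Outcomes section gives "Percentage of women achieving 48 hours pregnancy prolongation", with no time zero of its own. The section on data analysis and sample size rewords this: "Our primary outcome is the percentage of women that remain pregnant at >48 hours". Again it names no starting point. Among the Secondary Outcomes, the interval is "Number of hours from first dose of tocolytic agent to delivery".

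On who is randomised, Study Design says: "Consenting subjects will be randomly allocated to receive one of two clinically accepted clinical regimens". The same section gives the blinding: "We propose an open label, randomized, comparative effectiveness controlled trial". Under Randomization, the regimen is on paper in a numbered opaque envelope kept on the obstetrical unit.

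The document contains no intention-to-treat, modified intention-to-treat or as-treated statement. It has no rule for a woman who is randomised but receives no dose.

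**The concern.** The primary outcome takes its clock from the Objective, and that clock starts with treatment. Randomisation comes before treatment. A woman may deliver before the first dose, be found ineligible, withdraw, or have a physician who declines the opened regimen. She is then part of the randomised comparison but has no starting time under the plan's definition.

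Two features keep this from being a mere technicality. First, the choice to dose is made with the allocation known, and only one arm contains indomethacin. The risk section lists fetal concerns for indomethacin and says nifedipine has no direct fetal effects, so there is a plausible arm-specific reason to decline one envelope. Second, a woman who delivers before dosing is a failure if counted from randomisation, so leaving her out removes a failure rather than a random woman.

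With 40 per arm, each woman is 1/40 = 2.5 percentage points. Without a rule, whether to count her could be settled after the results are known.

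**Working it through.** **Inputs from the plan (Design prior distributions and the text below the table).** Control: "Single agent outcome rate: 77% (95% CI: 68%-85"%). Combination rate 95% (74% to 99.9%). Neutral prior RR 1.0 (0.5 to 1.33). Criterion Pr(RD>0.10) > 0.67. 40 per group, stated power 0.80.

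**Assumed prior forms.** The plan gives no distributional family, so these are my assumptions.
- Control: Beta(71.1, 21.2), with mean 77% and limits 68% to 85%.
- Combination design prior: Beta(7.75, 0.41), reading 95% as the mean.
- Neutral prior for the combination rate: Beta(4.38, 1.31), with mean 77% and lower limit 0.5 × 77% = 38.5%. The upper limit, 1.33 × 77% = 102%, cannot be matched by a proportion. A uniform prior was the alternative.

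**Formulas.** With x successes among n women, each arm's posterior is Beta(a + x, b + n − x). Then Pr(RD>0.10) = ∫ f_C(u) · [1 − F_T(u + 0.10)] du, where C is control and T is combination. Power is the beta-binomial predictive probability, under the design priors, that this exceeds 0.67.

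**Step 1: reproduce the plan's figure.** At n = 40 with a neutral analysis prior, power is 0.792 (Beta) or 0.791 (uniform), against the stated 0.80. With the enthusiastic prior it is 0.857 against 0.85. The match depends on reading 95% as a mean; read as a median, power is about 0.66 to 0.68. Other neutral forms (log-RR normal, or a Beta with median 77%) give 0.71 to 0.77, and flat priors in both arms give 0.695.

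**Step 2: one borderline result, control 31/40 (77.5%).** With everyone counted, the combination arm has 36/40 = 90.0% and RD = 12.5 points. With one failure dropped it has 36/39 = 92.3% and RD = 14.8 points.

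| Priors (control; combination) | 36/40 | 36/39 | Criterion 0.67 |
|---|---|---|---|
| Flat; flat | 0.59 | 0.70 | not met, then met |
| Beta(71.1, 21.2); Beta(4.4, 1.3) | 0.60 | 0.73 | not met, then met |
| Beta(71.1, 21.2); uniform | 0.58 | 0.72 | not met, then met |
| Beta(4.4, 1.3) in both arms | 0.55 | 0.65 | not met either way |

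In the last row, dropping a second failure (36/38) gives 0.75, which meets the criterion.

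**Step 3: the other direction.** Dropping one control-arm failure instead (31/39 against 36/40) lowers the probability to 0.50 (flat), 0.56 (informative control with Beta combination) and 0.45 (weak in both arms). Dropping one failure from each arm gives 0.61, 0.70 and 0.56.

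**Step 4: how often a result is this close.** The decision was recomputed for every possible 40 + 40 result under the neutral Beta and uniform forms with informative control. Dropping one combination-arm failure changes the decision in 32 to 35 of the 41 × 41 = 1,681 possible pairs. Those pairs have a total probability of about 0.10 to 0.125 if the true rates are 77% and 95%, and 0.05 to 0.06 under the design priors. These probabilities take it as given that such a woman exists.

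**The case against.** The strongest reply is that the plan is silent rather than wrong. No section defines the analysed women by dosing. The Objective's wording by regimen received is loose, and Study Design speaks of random allocation, which fits analysis as randomised just as well. An undosed woman's delivery time is observable, and the analysis section's wording of the primary outcome could be scored from randomisation. The explicit first-dose clock in the outcome lists belongs to a secondary interval, where it does little harm.

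Exposure is also narrow. Women are approached only after the physician has judged treatment necessary, those with known adverse effects to either drug are excluded, and the first dose is scheduled at 0 minutes. The example sits just below the threshold: at about the plan's own rates, 31/40 against 38/40 gives 0.86, 0.81 or 0.77 depending on the prior, so the criterion is already met.

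Most of this stands, and it limits the point. A reader might infer that the plan restricts the analysis to dosed women, or that an undosed woman has no outcome. The documents do not say either. What remains is that the only stated definition of prolongation starts at treatment, and that nothing says how a woman without treatment is counted.

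**Conclusion.** The gap is real and worth closing, but its likely effect is modest. Read literally, the plan gives an undosed woman neither a time zero nor a place in the denominator, and it leaves room to exclude her once her arm is known. In a borderline result one such exclusion can reverse the decision: from about 0.59–0.60 to 0.70–0.73 under flat or informative-control priors. Under weak neutral priors in both arms it takes two.

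This rests on assumed prior forms, on at least one woman going undosed, and on a result near the threshold. It would be tempting to conclude that the trial is biased towards the combination. The documents do not support that. They give no rate of undosed women and no evidence that exclusions would differ by arm, and losing a control-arm failure pushes the result the other way.

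**What to change.** In the Objective, the outcome sections and the analysis section, state that:

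- all randomised women are analysed in their assigned arm, whether or not a dose was given;
- the 48-hour, 7-day and interval clocks start at randomisation, with the envelope-opening time recorded;
- delivery before dosing counts as failure of the 48-hour and 7-day outcomes, and other undosed women are scored by their delivery time from randomisation;
- time from first dose is kept as a descriptive variable.

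The first and third items do most of the work. For women dosed promptly, moving the clock should change very little. The cost is a few sentences, one extra timestamp, and a slight dilution of any treatment effect by undosed women. No dose, schedule or clinical rule changes.

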#### *Nifedipine*

Nifedipine is a category C medication and is generally well tolerated. There are no associated teratogenic abnormalities in human pregnancies. The most frequently reported side effect in pregnancy is headache (7.5-31.2%) which is associated with transient hypotension caused by loading doses. Other reported adverse effects include flushing/heat sensation (5-43.7%), dizziness/lightheadedness/giddiness (6-27%), weakness (12%), nausea (11%), muscle cramps (8%), peripheral edema (7%), nervousness/mood changes (7%), palpitations/tachycardia (7%), dyspnea (6%) and nasal congestion/sore throat (6%). Nifedipine does not appear to influence fetal movement, heart or blood flow and thus does not have any direct fetal effects. In pregnancies with multiple gestations, nifedipine has been associated with increased dyspnea.

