#### *Indomethacin*

Indomethacin is a category C medication. Fetal exposure to indomethacin is associated with the development of antenatal closure of the ductus arteriosus, antenatal oligohydramnios, postnatal persistent patent ductus arteriosus, necrotizing enterocolitis, intraventricular hemorrhage and postnatal renal failure as reported clinically and in studies in rodents. Many of these adverse events occur with prolonged courses of indomethacin administered for both greater than 48 hours and over 32 weeks gestation. Other potential risks include nausea/vomiting/heartburn/abdominal discomfort (3-9%) and headache (11.7%).

Although employed in clinical practice at times, combination nifedipine-indomethacin has not been studied within a randomized controlled trial. Prior studies have raised concern for combination tocolytic agents due to reported cases of pulmonary edema, myocardial infarction and cardiovascular collapse. However, these included ritodrine, magnesium and terbutaline, which as individual agents increase this pulmonary risk. Thus, these risks are minimal with our study combination regimen.

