### **Neonatal follow up**

Neonatal follow up in the study will not differ from the follow up of neonates whose mothers received single tocolytics. Neonates receive routine follow up by the pediatrician or neonatologist if the admitted to the neonatal intensive care unit (NICU). If neonatal exam is concerning in an infant antenatally exposed to indomethacin (hypotension, cardiac murmur that does not resolve), an echocardiogram will be obtained at that point to assess the ductus arteriosus. There are no known fetal effects of nifedipine. Enrollment in the study will not incur extra time commitment for mother or baby aside from the initial 48 hours to administer tocolytic therapy.

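### Does the lack of a sibling rule for neonatal outcomes, when twins are eligible, call for a change to the plan?

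*Combined protocol and SAP*

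**What the plan says.** Under Inclusion Criteria: "We will include pregnant women with singleton or multiple gestation". The Nifedipine risk section also expects such pregnancies: "In pregnancies with multiple gestations, nifedipine has been associated with increased dyspnea".

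Secondary Outcomes lists "Neonatal outcomes including birthweight, gender, need for NICU admission, length of NICU admission, length of hospital stay, rate of death", continues with "intraventricular hemorrhage, necrotizing enterocolitis, culture positive sepsis, neonatal seizures" and several measures of respiratory support, and follows infants to discharge or day 120 of life. It gives no denominator and no rule for siblings.

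The Primary Outcomes section, and the opening of the data analysis section, define the primary outcome as a percentage of women. The only analysis described anywhere is the Bayesian comparison of those two percentages, under Design prior distributions. No method is given for any secondary outcome, neonatal or maternal.

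Some other sentences are worded for one infant per woman: "Cord blood (20 ml) will also be obtained at the time of delivery after delivery of the newborn" and "once the neonate and placenta are delivered" under Pharmacogenomics, and "Enrollment in the study will not incur extra time commitment for mother or baby" under Neonatal follow up.

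**The concern.** The woman is randomised, but a twin pregnancy yields two infants who share a mother, a gestational age at delivery and a drug exposure. If the two-percentage comparison used for the primary were applied to infants, siblings would count as independent and the intervals would be too narrow.

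The unit also affects the estimate. A pregnancy with two affected twins counts twice per infant and once per mother, so the same data can give two risk differences.

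The outcomes are not trivial. The Indomethacin section says "Fetal exposure to indomethacin is associated with the development of antenatal closure of the ductus arteriosus", and the same sentence goes on to necrotizing enterocolitis and intraventricular hemorrhage. Both are listed neonatal outcomes, and indomethacin is the drug that differs between the arms. The trial is open label and small, so one or two affected twin pairs could shift such a comparison.

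**Working it through.** **The plan's own figure.** The plan gives no figure for a neonatal outcome. Its one design figure is 80% power at 40 women per group for Pr(RD > 0.10) > 0.67. With rates fixed at 77% and 95%, and the neutral prior read as Beta(71.1, 21.2) for control and Beta(4.75, 1.6) for combination, simulation gave 0.80–0.82 at n = 40. Drawing the rates from the design priors gave 0.67–0.68. The plan does not state the form of its priors, so the figure is neither confirmed nor refuted. It counts women, so no sibling term enters it.

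**Inputs.** From the documents: 40 women per arm, multiples eligible. Assumed, because the documents are silent: twin share s = 0.1, 0.2, 0.3, paired with sibling correlation ρ = 0.3, 0.45, 0.6.

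**Variance inflation from ignoring siblings.** True variance over naive variance is

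[(1 − s) + 2s(1 + ρ)] / (1 + s).

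- s = 0.1, ρ = 0.3: (0.9 + 0.26)/1.1 = 1.055
- s = 0.2, ρ = 0.45: (0.8 + 0.58)/1.2 = 1.150
- s = 0.3, ρ = 0.6: (0.7 + 0.96)/1.3 = 1.277

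The standard-error ratio r is the square root. The naive standard error is too small by 1 − 1/r. Effective infants are 40(1 + s) divided by the variance ratio. Coverage is from simulations of 40,000 trials per setting, with 10% infant risk and no true difference.

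| s, ρ | r | Naive SE too small by | Infants per arm | Effective infants | Coverage of naive 95% interval |
|---|---|---|---|---|---|
| 0.1, 0.3 | 1.027 | 2.6% | 44 | 41.7 | 0.936 |
| 0.2, 0.45 | 1.072 | 6.7% | 48 | 41.7 | 0.925 |
| 0.3, 0.6 | 1.130 | 11.5% | 52 | 40.7 | 0.911 |

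At 30% risk coverage was 0.935, 0.926 and 0.911; for a continuous outcome it was 0.940, 0.926 and 0.913. Clustering on the mother gave 0.947–0.952. Correct intervals are therefore 3–13% wider than naive ones. Stretching ρ to 0.2–0.9 gives a variance ratio of 1.04–1.42 and naive standard errors 2–16% too small.

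**Choice of unit.** With no true difference, the per-infant risk difference and the any-affected-infant-per-mother risk difference were more than 2 points apart in 6%, 13% and 20% of trials at 5% risk, and in 14%, 28% and 36% at 10% risk. They had opposite signs in 0.5–2.2% and 0.9–3.9%.

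**An unfavourable example** (assumed: 8 twin pairs per arm). Combination arm: 3 affected singletons and both infants of 2 pairs. Control arm: 2 affected singletons.

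- Per infant: 7/48 − 2/48 = 14.6% − 4.2% = 10.4 points; posterior probability of a higher rate 0.95 with uniform priors.
- Per mother: 5/40 − 2/40 = 12.5% − 5.0% = 7.5 points; probability 0.87.

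Both point the same way.

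**The case for a change.** The best case for a change is that necrotizing enterocolitis and intraventricular hemorrhage are the neonatal harms the protocol itself ties to the added drug. Events will probably be few and treatment is known to the investigators. A unit chosen after seeing the data could be doubted, since 0.95 and 0.87 from the same infants read differently. One sentence and a mother identifier on each infant record would settle it at no cost in patients.

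Much of this stands. The omission is real, the arithmetic holds, and a report should state the unit and the number of multiple pregnancies in each arm.

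It does not show an error in the plan. Siblings would be treated as independent only if the primary's method were carried over to infants, which the plan nowhere says. The list itself leans towards the infant as unit: birthweight, gender and day of life belong to a child. The singular wording elsewhere concerns specimen timing and families' time, not analysis. The missing sibling rule is one instance of a plan that leaves all secondary analyses unspecified.

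More elaborate rules would not clearly help. For example, switching to a per-mother count when fewer than ten infants are affected would, at 10% risk, select the per-mother count in 61%, 51% and 42% of trials in the three settings. The data would then choose the unit, and two harms in one trial could be reported on different bases.

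**Conclusion.** No change to the plan follows. This is missing detail on secondary outcomes that an analyst fills sensibly: count infants, allow for correlation within the mother, and use the same unit for every neonatal outcome. No stated rule yields a wrong result.

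Even if siblings were ignored, 95% intervals would still cover 91–94% under the main assumptions. The choice of unit matters more than the clustering for rare events, yet it would seldom reverse a direction. These sizes rest on the assumed twin share, sibling correlation and event risks. The conclusion that sibling correlation leaves the primary outcome and sample size untouched needs no assumption, because both count each woman once.
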